Families will be recruited from pediatric practices in our Practice-based Research Networks (PBRNs) in several ways. Each practice will have children who meet age, height, and weight criteria flagged in their charts, and we will use multiple approaches to recruit families. First, we will establish a ResearchMatch approach to recruiting in each PBRN. ResearchMatch, an online recruitment tool, will accrue families in one of two ways. At intake for a well- or sick-child visit, forms designed to acquaint families with the study will be introduced by PLAN coaches, and families can sign up for additional information about this study. Their information will be entered into a database by the PLAN coaches, and they will be contacted if they meet criteria. In addition, we will set up a website that they will be directed to in a flyer, and they can sign up to participate from the website. Since the pediatrician generally will not have information on parental health, this will need to be collected prior to deciding study eligibility, and the family database will assist in this endeavor by including information about all family members after a phone screen is conducted by the PLAN coaches with the participating parent. Second, PBRN practices post study advertisement at offices for interested families to visit the study website to complete questionnaires to ensure they meet eligibility criteria. If the families meet eligibility criteria, a PLAN coach will follow up with the families to schedule their first appointment at their earliest convenience. At this appointment, the PLAN coach will confirm the families' interest to participate and eligibility prior to participation. Third, Plan coaches will meet with families during well-child visits to introduce the study, assess their interest, and explain next steps. Each of these methods in collecting their information regarding interest and eligibility will be preceded by getting their verbal consent over the phone or a check box indicated on the web pages.

During recruitment, PLAN coaches will explain that there is a 50/50 possibility of getting one treatment over the other treatment. This will be like a flip of the coin and no one can just pick one treatment or the other. This study is testing if the FBT is as good as the care provided by their doctors normally given or better. Randomization will occur after the first appointment.

Inclusion Criteria

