With the above comments in mind and with the focus of the study being on a between-group comparison of the change from baseline to 24 months, the primary analysis will be an analysis of covariance with the 24-month value as the dependent variable and with the baseline value as a predictor variable. The statistical model we employ reflects the parametrization described by Baldwin and Colleagues.⁶⁰ It takes the initial form $Y_{24ij} = \beta_{0j} + \beta_{1j}X_{ij} + Y_{0ij} + e_{ij}$. In this model, Y_{24ij} is the 24-month value of the percent over the age and sex matched 50th BMI percentile (the primary outcome) for subject i and cluster j , with the “clusters” being defined by the coach in the intervention group and by individual children in the control group; β_{0j} and $\beta_{1j}X_{ij}$ are the intercept and intervention effect for cluster j ; Y_{0ij} is the baseline value of the outcome measure; and e_{ij} is the normally distributed error term. *In these models, the intercept and baseline are fixed effects while the intervention effect is random (DSMB approved protocol addenda, 11.2.18).* To reflect the partial clustering structure of the IRGT design, the above expression is modified by using the cluster-level equations $\beta_{0j} = \lambda_{00}$ and $\beta_{1j} = \lambda_{10} + \mu_{1j}$ to describe how the coefficients β_{0j} and β_{1j} vary across clusters. *The reparametrization of β_{1j} yields two random effects (DSMB approved protocol addenda, 11.2.18)* and the term μ_{1j} permits between-cluster variability in the outcome measure only within the intervention group (coded as 1). Substituting in the initial equation above yields the final model:

$$Y_{24ij} = \lambda_{00} + \lambda_{10}X_{ij} + \mu_{1j} X_{ij} + Y_{0ij} + e_{ij}$$

Using PROC MIXED in SAS, separate covariance structures will be fit to the FBT group and the UC group to account for the fact that the coach is nested within the site in the FBT group while there is no such nesting in the UC group. All analyses other than the above are secondary or exploratory analyses. One of those secondary analyses will supplement the primary analysis by adjusting for the sex and race of the participating child, family income, the educational level of the participating parent, and whether there are one or two parents in the household. These secondary analyses will provide insight regarding the impact the covariates may have on the primary outcome.

1. Sample Size and Statistical Power

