Power computations for PLAN employ simulations and two-sided tests at the 0.05 level of significance. The simulations reflect the planned primary analysis of covariance and the fact that this is an individually randomized group treatment trial with the coach (N=3 per site) nested within the site (N=4 sites) in the FBT group but with no such nesting in the UC group. The analysis of covariance that is simulated in the power computations treats the 24-month value of the outcome measure as the dependent variable and the baseline value as a covariate. The use of this approach reflects the primary study goal of comparing 24-month values across groups, with the outcome being compared being percent over normalized BMI in the participating child. Each result is based on 1000 simulations.

Tabulated power values employ sample sizes of 528 and that are between 65% and 95% of that total. Effect size estimates are generated using considerations and preliminary data discussed below. Usual care data involving an intervention and subjects most similar to our UC group is provided by Kalarchian⁶¹ who randomized 81 8-12-year-old children with obesity to a usual care control condition and found an average percent overweight change of -0.17 ± 10.08 at 1 year. We expect some deterioration in this group at 2 years but will assume conservatively for the purpose of power computations that the two-year change will be 0 ± 10.08 in the UC group in the proposed research. Our estimated change in the FBT group begins with a review of seven studies^{20,62-67} authored by [name]. There were 314 overweight/obese children in those studies who received FBT interventions similar to the one we will employ. When we combined

the data for those 314 children, we found an overall average decrease in percent over BMI of 10.6 ± 15.3 at 24 months.

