Computations are for the primary outcome which is the percent over the 50th percentile of BMI in children. Results are generated using 1000 simulations of the primary analytic model: an analysis of covariance with the 24-month value as the dependent variable and the baseline value as a covariate. The analysis reflects the fact that this is an individually randomized group treatment trial in which the coach is nested within the site within the FBT group but which is different from a classic cluster randomized trial in that there is no such nesting within the control (UC) group. The total number of randomized families is assumed to range from 65% to 100% of the target of 528. Tabulations assume an ICC of 0.01 in the UC group and of 0.04, 0.06, 0.10, and 0.15 in the FBT group, mean differences of 5.3, 6.4 and 7.4 (which represent 50%, 60%, and 70% of observed results in previous studies), and standard deviations of 12.7 and 15.3.

(N's Adjusted Below, DSMB approved protocol addenda, 9.29.19).

ICC		SD	Mean diff	Statistical power associated with sample sizes ranging from 65% to 100% of original target of 528							
FBT grp	UC grp			N=528 (100%)	N=502 (95%)	N=476 (90%)	N=449 (85%)	N=422 (80%)	N=396 (75%)	N=370 (70%)	N=344 (65%)
0.04	0.01	12.7	5.3	0.95	0.95	0.94	0.92	0.93	0.92	0.89	0.89
			6.4	0.99	0.98	0.99	0.98	0.99	0.98	0.98	0.97
			7.4	1.00	1.00	1.00	1.00	1.00	1.00	0.99	1.00
		15.3	5.3	0.84	0.83	0.83	0.81	0.80	0.76	0.76	0.74
			6.4	0.96	0.94	0.95	0.92	0.91	0.91	0.88	0.87
			7.4	0.99	0.99	0.99	0.98	0.97	0.97	0.97	0.96
0.06	0.01	12.7	5.3	0.92	0.91	0.90	0.90	0.88	0.87	0.85	0.84
			6.4	0.98	0.98	0.98	0.98	0.97	0.96	0.95	0.95
			7.4	1.00	1.00	1.00	1.00	0.99	0.99	0.99	0.99
		15.3	5.3	0.80	0.79	0.77	0.78	0.74	0.73	0.70	0.68
			6.4	0.92	0.91	0.92	0.91	0.88	0.87	0.85	0.84
			7.4	0.97	0.97	0.96	0.97	0.96	0.95	0.93	0.94
0.10	0.01	12.7	5.3	0.85	0.83	0.81	0.83	0.80	0.80	0.76	0.76
			6.4	0.95	0.94	0.94	0.93	0.91	0.92	0.91	0.88
			7.4	0.98	0.98	0.98	0.98	0.98	0.97	0.97	0.97
		15.3	5.3	0.69	0.68	0.69	0.63	0.67	0.65	0.62	0.60
			6.4	0.84	0.82	0.84	0.81	0.81	0.77	0.76	0.78
			7.4	0.94	0.94	0.92	0.92	0.91	0.89	0.89	0.87
0.15	0.01	12.7	5.3	0.73	0.75	0.71	0.72	0.69	0.70	0.70	0.68
			6.4	0.86	0.85	0.83	0.85	0.85	0.84	0.83	0.81
		7.4	0.95	0.95	0.95	0.94	0.94	0.93	0.93	0.92	
			5.3	0.57	0.59	0.55	0.56	0.53	0.53	0.52	0.52

[figure not shown]
		15. 3	6.4 7.4	0.73 0.86	0.74 0.82	0.70 0.86	0.73 0.83	0.71 0.82	0.67 0.81	0.68 0.80	0.65 0.79

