- c. If there is no clinic visit within 30 days of the 24-month target but there are visits both before and after the 24-month time point, we will interpolate linearly between predicted height and weight values at those time points to determine the predicted 24-month value. *Because we will only employ this option if height and weight data are available no more than three months before and three months after the target date for the 24-month visit, we anticipate that this interpolation approach will be performed infrequently in practice (DSMB approved protocol addenda, 11.2.18).*

3. If the 24-month value of height and/or weight is missing and the child did not have height and weight data collected by his or her pediatrician at a clinic visit that took place within 30 days of the planned 24-month assessment and did not have height and weight data measured at the clinic *within three months* both before and after the targeted 24-month visit, the 24-month value will be imputed using multiple imputation (*DSMB approved protocol addenda, 11.2.18*). Variables that will be used to facilitate the imputation process will be baseline height and weight, age, sex, and race. Any height and weight data collected using PLAN assessments at 6, 12, or 18 months will also be included in the multiple imputation.

Two points about the methods discussed in this section are in order. First, the rational for using multiple imputation only after it has been determined that clinic visit data are not available as a vehicle for imputing values is as follows. We anticipate that while values measured at the clinic will not employ the same rigor that will be employed in our protocol governed visits every six months, it is likely that the magnitude of the error will be relatively small and probably systematic rather than random within clinics. We therefore anticipate that this use of real measured data will yield more accurate results than multiple imputation. This is especially so for individuals who provide no data beyond their baseline measurement.

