While the above sample size may not provide the robust statistical power that would be ideal, we emphasize that this is a secondary aim that will study by far the largest number of overweight/obese siblings ever evaluated in this setting. Thus, this aim will provide a unique set of data that will yield valuable insights into whether FBT may benefit non-participating siblings while generating preliminary effect size data to guide future studies. A positive finding would provide a compelling incentive for the future dissemination of FBT to family practices. In cases where more than one eligible sibling is available, we will enroll the sibling whose age is closest to that of the study child. Data analyses will reflect the wide age eligibility range for siblings and current uncertainty regarding the impact of sibling age on outcome. We will address this uncertainty by adjusting for sibling age and whether the sibling is older or younger than the participating child, with particular concern for the possibility that sibling age may have a non-linear relationship with FBT effectiveness. The wide age eligibility range for siblings reflects our desire to maximize information generated about this population and the limited resource expenditure

that is required to study these non-participants. We will also adjust for whether the sex of the sibling is the same as that of the targeted child since prior data suggest that same sex siblings respond better than opposite sex siblings.¹⁹

E. Analysis of Secondary Aim 3 (DSMB approved protocol addenda, 11.2.18).

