3. A per protocol dataset will be defined as including all subjects who attend at least 80% of the prescribed sessions. Sensitivity analyses will assess whether applying the primary analysis to the per protocol dataset yields the same result as the primary ITT analysis. *All control group subjects who do not drop out of the study will be considered to be part of the per protocol dataset. We recognize that this implies a somewhat different definition in the two study arms. But we do not consider this to be a problem since this is a sensitivity analysis whose goal is to repeat the primary analysis in a different setting (DSMB approved protocol addenda, 11.2.18).*
4. Random coefficient models that potentially use different covariance structures in the two study arms will include all primary outcome data collected at baseline, 6, 12, 18, and 24 months. Since weight change often occurs at a more rapid rate early in a weight loss study, these sensitivity analyses will include an exploration of non-linear possibilities such as quadratic models. They will also assess contrasts that compare changes from baseline to 24 months across groups in order to use an alternative model for testing the central hypothesis of the primary analysis.
5. Repeat the primary analysis after adjusting for baseline covariates. The covariates to be used are the race and sex of the participating child, family income, the educational level of the participating parent, and whether there are one or two parents in the household.

F. The Time Between Randomization and the Measurement of the Primary Outcome

The time between randomization and the measurement of the primary outcome will vary among participants and will potentially differ between groups. Our approach to addressing the potential impact of this reality is described below.

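### The index child's baseline age is missing from the covariate list for the adjusted child-outcome analyses; adding it is a small, nearly free improvement

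*Combined protocol and SAP*

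**What the plan says.** The primary model (III.B) is an ANCOVA of 24-month percent over BMI with its baseline value as the only covariate. The outcome is expressed relative to the median BMI for the child's age and sex.

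Three further analyses of the child outcome share one covariate list:

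- III.B, supplementary analysis: "adjusting for the sex and race of the participating child, family income, the educational level of the participating parent", and whether the household has one or two parents. Its stated purpose is to show how covariates bear on the primary outcome.
- III.B.3, longitudinal models: the list is taken over by reference.
- III.E, sensitivity analysis 5: "The covariates to be used are the race and sex of the participating child, family income", then parental education and number of parents.

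Section III.F may add time to the final assessment. Secondary Aim 4 brings in parental inconsistency and environmental enrichment. Neither adds the index child's age.

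Age does appear elsewhere. Screening computes it from the birth date (Table 2 footnotes). The clinic-based imputation in III.B.7 uses it to predict height and weight. For the multiple imputation, "Variables that will be used to facilitate the imputation process will be baseline height and weight, age, sex, and race". The sibling analysis (Secondary Aim 2) provides for "adjusting for sibling age and whether the sibling is older or younger than the participating child".

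**The concern.** Age is a natural baseline variable to list for children who enter at 6 to 12 and are about 8 to 14 at the end of follow-up. The plan lists sex but not age and gives no reason. The outcome is standardised for both, so standardisation cannot be why one is kept and the other left out.

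Two modest things are at stake. First, analyses meant to show the influence of covariates omit an evident candidate, and age added after results are known would be post hoc. Second, if age predicts the 24-month value beyond the baseline value, leaving it out of the primary model gives up some precision.

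**Working it through.** **Is age absent?** Set side by side, the primary model, the III.B list, the III.B.3 reference to that list, III.E item 5, the possible addition in III.F and the Secondary Aim 4 covariates contain no term for the index child's age.

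**Inputs for the size of the effect**

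- Test: "two-sided tests at the 0.05 level of significance" (Sample Size and Statistical Power).
- Size: "Tabulated power values employ sample sizes of 528", among others. Families are told "there is a 50/50 possibility of getting one treatment over the other treatment", so 264 per arm.
- Effect: "mean differences of 5.3, 6.4 and 7.4"; 5.3 is used here.
- SD: 12.7 or 15.3. ICC: 0.01 in UC and 0.04 to 0.15 in FBT.
- Coaches: 3 at each of 4 sites, so 12.
- Assumed: r, the partial correlation of baseline age with the 24-month outcome given the baseline outcome. The documents do not report it, so 0.1, 0.2 and 0.3 are shown.
- Assumed: the UC ICC acts over 12 notional groups, because the plan does not say how it was simulated.

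**Reproducing the plan's figure.** Take the stated SD as the residual SD and use a noncentral t with 12 − 1 = 11 df:

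Var = SD² × [ICC_F/12 + (1 − ICC_F)/264 + ICC_U/12 + (1 − ICC_U)/264]

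For SD 15.3 and FBT ICC 0.04:

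- Cluster part: (0.04 + 0.01)/12 = 0.004167
- Individual part: (0.96 + 0.99)/264 = 0.007386
- Var = 234.09 × 0.011553 = 2.704, so SE = 1.645
- Power for a difference of 5.3 is 0.834; the power table gives 0.84.

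With SD 12.7 the same steps give 0.941 against 0.95. At 528 families, all 18 cells with FBT ICC 0.04 to 0.10 agree within 0.02. At ICC 0.15 the formula runs 0.03 to 0.04 high in 4 of 6 cells, so that ICC is not used here. Leaving out the UC ICC would give SE 1.587 and power 0.859, further from the table, so it is kept.

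**Adding age to the primary ANCOVA.** Age removes a share r² of the individual-level variance and is taken to leave between-coach variance unchanged:

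Var(r) = SD² × [0.004167 + 0.007386 × (1 − r²)]

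For r = 0.3: 234.09 × (0.004167 + 0.006722) = 2.549, so SE = 1.597.

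| r (assumed) | SE | Fall in SE | Power | Gain, points |
|---|---|---|---|---|
| 0 (current) | 1.645 | – | 0.834 | – |
| 0.1 | 1.639 | 0.3% | 0.837 | 0.2 |
| 0.2 | 1.623 | 1.3% | 0.844 | 0.9 |
| 0.3 | 1.597 | 2.9% | 0.855 | 2.1 |

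(528 families, difference 5.3, SD 15.3, FBT ICC 0.04; gains are from unrounded values.) At FBT ICC 0.10 power goes from 0.695 to 0.712 at r = 0.3, a gain of 1.7 points, because the coach component is a larger share of the variance.

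**Adding age only to the secondary and sensitivity lists.** The primary model is unchanged, so primary power is unchanged.

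**The case against.** The strongest reply is that the outcome is already age-standardised and its baseline value is in the model. Age can then help only through a residual correlation that the documents never report. This stands, and it is why the gain is given as an assumed range. It does not explain why sex, which is standardised in the same way, is listed.

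The uses of age elsewhere also prove less than they seem to. Imputation predicts raw height and weight in growing children, where age is needed whatever the analysis model contains; using it there and not in the ANCOVA is not an error. Sibling age is adjusted for because siblings range from 2 to 18 years, a wider span than 6 to 12. Both replies are fair. What remains is that age is on hand and no reason is given for leaving it out.

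The possible gain is also small beside the noise in the power table: with 1000 simulations, a cell at 0.84 carries a 95% Monte Carlo error of 1.96 × √(0.84 × 0.16/1000) = 0.023.

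Stronger readings are tempting and are not supported:

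- A reader might infer that chance age imbalance could bias the estimate. The documents give neither the SD of age nor an outcome slope per year. Chance imbalance is already part of the unadjusted standard error, so counting it separately would count the same gain twice.
- A reader might infer that the omission leaves age differences in spread or in treatment response uncorrected. The documents show no such differences, and an age main effect would correct neither; that would take a variance model or an interaction term.

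**Conclusion.** The omission is confirmed: the index child's baseline age is in no covariate set for the child outcome. This is a minor improvement to the plan and not an error. The primary ANCOVA is valid as written, and the documents do not support a reading that its power is materially understated or its estimate biased for want of age.

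The adjusted analyses would serve their stated purpose better with age listed. The primary result gains only if age enters the primary model, and then probably little: a standard error about 0.3% to 3% lower and roughly 0.2 to 2 power points in the scenario worked above. That rests on an assumed partial correlation of 0.1 to 0.3, on age leaving between-coach variance unchanged, and on an analytic approximation that matches the plan's simulated power to within 0.02 over the ICCs used.

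**What to change.** Add the index child's age at baseline, as a continuous variable, to the covariate list in III.B and in III.E item 5. III.B.3 follows by reference and needs no edit. If the amendment is made before unblinding, also add age to the primary ANCOVA beside baseline percent over BMI. After unblinding, leave the primary model alone and label any age-adjusted result post hoc. If the sponsor prefers to omit age, one sentence should say why sex is kept and age is not.

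The cost is one degree of freedom per model and a few words of SAP text. No new data are needed, and age is already among the multiple-imputation variables. The power table can stand, since it would be slightly conservative if age has any predictive value.

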In translating the above decrease of 10.6 ± 15.3 in percent over BMI at 24 months into the setting of the proposed research, we emphasize that the seven referenced studies implemented FBT in controlled academic settings where we anticipate better performance than is likely in the family practices we will employ in this study. To estimate the degree to which the effect is likely to be attenuated when we switch from highly controlled to more “real life” settings, we considered the following. The child weight management intervention MEND (Mind, Exercise, Nutrition, Do it) focused on children age 7-13 who exceeded the 91st weight percentile. MEND employed both (1) a community-based mass-implementation intervention⁶⁸ involving many programs and 9563 subjects who provided complete data and (2) a rigorous randomized trial⁶⁹ (N=116) analogous to the seven [name] studies referenced in the preceding paragraph. The 12-month results were reductions in BMI of 0.79 kg/m^2 in the community study as compared to 1.04 kg/m^2 in the intervention arm of the randomized trial. Thus, the reduction in the community-based MEND intervention was 76.0% of the magnitude that was observed in the family-based arm of the randomized trial.

Based on this 76.0%, our computations conservatively assume changes in the intervention group that are 50%, 60%, and 70% of the previously observed change of 10.6 ± 15.3 that was observed in the rigorous academic environment of [name] studies.^{20,62-67} Thus, we base our power on a comparison of projected reductions of 5.3 ± 15.3 (50% of 10.6 ± 15.3), 6.4 ± 15.3 (60% of 10.6), and 7.4 ± 15.3 (70% of 10.6) in the FBT group as compared to 0 ± 10.08 in the UC group. In addition, given projected standard deviations of 15.3 and 10.08 in the two groups, we use the maximum and the mean of those two values and thereby compute power assuming standard deviations of both 15.3 and 12.7. In performing the calculations summarized below, we emphasize that we will have actual or imputed 24-month data on all subjects. To see details of how we will impute the 24 month values when necessary, please see the section below titled “Implementation of the Intention-to-Treat Principle.”

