Table 1 contains the results of the power computations using the parameters discussed above, assuming the compound symmetry covariance structure in both study arms and assuming an intraclass correlation coefficient (ICC) in the UC group of 0.01 and ICCs in the FBT group of 0.04, 0.06, 0.10, and 0.15. We assume a small ICC in the UC group of 0.01 because there is no clustering within that group meaning that the ICC should be essentially zero. While we do not have data with which to estimate the ICC in the FBT group, we note that many cluster trials that involve group interventions have reported ICCs in the 0.01 to 0.05 range. Since the PLAN intervention is individualized and since we expect PLAN children to have no contact with one another, we do not face the impact on the ICC that is present in many cluster trials. This argues for a very small ICC in the FBT group. By contrast, the fact that the same coach will be responsible for multiple children will inevitably increase the ICC above where it might otherwise be. Based on these considerations, we tabulate power for ICCs in the FBT group that range from 0.04 to 0.15. However, the many other studies that have used group interventions while yielding ICCs below 0.05 suggests that the ICC ultimately observed in PLAN will be substantially less than 0.1.

Results in Table 1 indicate that if we recruit 100% of our original target of 528 families, power will be excellent for all tabulated scenarios with an ICC in the FBT group of 0.1 or less. For an ICC

no bigger than 0.1, power remains adequate for most scenarios if we recruit at least 80% of the target (N = 432). If recruitment is below the 80% figure, an adequate power of at least 0.8 requires either the smaller of the two tabulated standard deviations or a mean difference that is at least 60% of the value observed in [name] studies (difference at least 6.4).

Table 1: Statistical power for two sided tests at the 0.05 level of significance.

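### The usual-care SD of 10.08 is a 1-year figure used, without justification, for the two-year change, so the SD 12.7 rows of the power table may be optimistic and the text should lead with the SD 15.3 rows

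*Combined protocol and SAP*

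**What the plan says.** The primary outcome is the child's percent over BMI at 24 months (III.B, Primary Analysis). III.B.1, Sample Size and Statistical Power, takes its UC inputs from the usual-care arm of one external trial (81 children with obesity), which "found an average percent overweight change of -0.17 ± 10.08 at 1 year". The plan expects this group to deteriorate by year 2, but it will "assume conservatively for the purpose of power computations that the two-year change will be 0 ± 10.08 in the UC group".

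The FBT input comes from 314 treated children in seven studies: "we found an overall average decrease in percent over BMI of 10.6 ± 15.3 at 24 months".

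The two SDs are then combined: "we use the maximum and the mean of those two values and thereby compute power assuming standard deviations of both 15.3 and 12.7". Every scenario in Table 1 of III.B.1 is shown at both values.

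The paragraphs just before Table 1 describe power at full recruitment as excellent in all scenarios with an FBT ICC of 0.1 or less. For recruitment below 80% they state that "an adequate power of at least 0.8 requires either the smaller of the two tabulated standard deviations or a mean difference" of at least 6.4.

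**The concern.** The 10.08 describes spread after one year, while the trial is powered for two. The plan discusses how the UC mean may move between those times and says nothing about the SD. If individual changes spread out further in the second year, 10.08 is too small, and so is the 12.7 built from it. The plan treats time as important elsewhere: III.B.7 regards a three-month shift in a visit as substantial in growing children, and here the gap is twelve months.

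The summary relies on the 12.7 rows. Below 80% recruitment, at difference 5.3, the smaller SD is the only route to 0.8 power: at N = 396 the SD 15.3 cells are 0.76, 0.73, 0.65 and 0.53. A reader is not told that this route depends on a 1-year figure.

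**Working it through.** **Inputs.** All are from III.B.1 unless noted.
- Two-sided 0.05, difference 5.3, N = 528.
- 264 families per arm (1:1 allocation, Recruitment section).
- 12 coaches (3 at each of 4 sites), so m = 264/12 = 22 families per coach.
- ICC 0.01 in UC, and 0.04, 0.06, 0.10 or 0.15 in FBT.
- SDs 15.3 (FBT, 24 months) and 10.08 (UC, 1 year). Their mean is (15.3 + 10.08)/2 = 12.69, printed as 12.7.

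**Formula.** Variance of an arm mean = SD² × [1 + (m − 1) × ICC]/264. SE = square root of the sum over the two arms. Power comes from a noncentral t with noncentrality 5.3/SE and 12 − 1 = 11 df. The change SD is used directly as the residual SD, with no allowance for baseline adjustment.

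**Step 1: reproduce the plan's figures (same SD in both arms).**

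| FBT ICC | SD 12.7 computed / printed | SD 15.3 computed / printed |
|---|---|---|
| 0.04 | 0.941 / 0.95 | 0.834 / 0.84 |
| 0.06 | 0.911 / 0.92 | 0.785 / 0.80 |
| 0.10 | 0.844 / 0.85 | 0.695 / 0.69 |
| 0.15 | 0.760 / 0.73 | 0.601 / 0.57 |

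The six cells with ICC up to 0.10 agree within 2 points. The two at ICC 0.15 are about 3 points high. That is about two simulation standard errors, since √(0.57 × 0.43/1000) = 0.016. The table follows from its stated inputs.

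**Step 2: change only the UC SD, with FBT held at 15.3.** The two-year UC SD is not in the documents. The assumed range runs from 10.08 (no change) through 12 and 14.26 (10.08 × √2, variance of change proportional to time) to 15.3 (equal to FBT).

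Example at ICC 0.04:
- FBT variance = 234.09 × 1.84/264 = 1.632.
- UC variance at 10.08 = 101.61 × 1.21/264 = 0.466. SE = √2.097 = 1.448, 5.3/1.448 = 3.66, power 0.914.
- UC variance at 15.3 = 234.09 × 1.21/264 = 1.073. SE = √2.704 = 1.644, 5.3/1.644 = 3.22, power 0.834.

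| FBT ICC | UC 10.08 | UC 12 | UC 14.26 | UC 15.3 | Loss from 10.08 (12 to 15.3) |
|---|---|---|---|---|---|
| 0.04 | 0.914 | 0.889 | 0.853 | 0.834 | 2.5 to 8.0 points |
| 0.06 | 0.866 | 0.840 | 0.804 | 0.785 | 2.6 to 8.1 points |
| 0.10 | 0.768 | 0.743 | 0.711 | 0.695 | 2.5 to 7.3 points |
| 0.15 | 0.660 | 0.640 | 0.614 | 0.601 | 2.0 to 5.9 points |

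**Step 3: set the summary text against the printed 15.3 rows.** At difference 5.3 and N = 528, power is 0.84, 0.80, 0.69 and 0.57 for the four ICCs. In the 80% column (N = 422) it is 0.80, 0.74, 0.67 and 0.53, so 0.8 is reached only at ICC 0.04.

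**The case against.** The strongest reply is that the plan already contains its own safeguard. Every scenario is printed at SD 15.3 in both arms. Those rows do not use 10.08, they cover any two-year UC SD up to 15.3, and the plan never names 12.7 as its planning value. This stands: the problem is bounded and no change of sample size follows from it. It does not rescue the summary text, which is not drawn from those rows.

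Second, the direction is not established. Nothing in the documents says that the spread of change widens between years 1 and 2 on an age- and sex-standardised measure. The source arm was children with obesity, whereas PLAN enrols from the 85th percentile, so 10.08 could be wrong either way. This also stands, and it limits the conclusion to what may be so.

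Third, Table 1 reproduces with no credit for baseline adjustment. With equal baseline and 24-month variances (an assumption), the ANCOVA residual SD is the change SD × √((1 + r)/2), or 0.92 to 0.97 of it for assumed r of 0.7 to 0.9. That would offset part of any loss. The plan gives no r, so it cannot be netted off.

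Fourth, 15.3 is not a UC estimate either, because it comes from treated children. It serves as a cautious bound and no more.

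**Conclusion.** A 1-year UC SD is used for a two-year change without justification, and it enters half of Table 1. The 12.7 rows may therefore be optimistic. Under an assumed two-year UC SD of 12 to 15.3, with FBT at 15.3, N = 528 and difference 5.3, the cost is about 2 to 8 points of power before any gain from baseline adjustment. If the true value is 10.08, the time point costs nothing. Separately from the time point, the printed 15.3 cell of 0.69 at ICC 0.10 does not fit a description of excellent power for all scenarios with ICC up to 0.1.

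A reader might infer more, in four ways that the documents do not support:
- That power is shown to be optimistic. No two-year UC SD is given.
- That the time point costs 11 to 16 points, the printed drop from the 12.7 rows to the 15.3 rows (0.95 to 0.84, 0.92 to 0.80, 0.85 to 0.69, 0.73 to 0.57). That drop assumes the top of the range and includes the separate effect of averaging the SDs across arms. At ICC 0.10 the computed fall from 0.844 to 0.768 is averaging, and only 0.768 to 0.695 is the UC SD.
- That the plan wrongly calls its SD conservative. In context the word follows the expected deterioration and concerns the mean.
- That the conditional power computations under Study Halting Rules would use 12.7. That section names no SD.

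**What to change.** In III.B.1:
1. State that 10.08 is a 12-month SD, that no two-year UC SD was available, and that the 12.7 rows therefore mix a 12-month UC SD with a 24-month FBT SD. Label them the more favourable case.
2. Make the 15.3 rows the cautious planning basis, noting that 15.3 comes from treated children and is a bound, not a UC estimate.
3. Rewrite the summary before Table 1 from those rows. At N = 528 and difference 5.3, power is 0.84, 0.80, 0.69 and 0.57 for FBT ICCs of 0.04, 0.06, 0.10 and 0.15. At N = 422 and the same difference, 0.8 is reached only at ICC 0.04. Remove the statement that power is excellent in all scenarios with ICC up to 0.1.
4. Keep the smaller SD as a route to 0.8 power only with the caveat that it rests on a 1-year UC SD.

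The cost is wording. The 15.3 rows are already printed, so no new simulations or participants are needed. The downside is that the stated power becomes less favourable.
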